9.2 SAMPLE SIZE DETERMINATION

The study plans to enroll 800 patients: 400 patients will be assigned to the test treatment and 400 to standard treatment.

A sample size of 362 patients in each group is required to assess the non-inferiority of the test treatment vs. the standard therapy (i.e. lower limit of the 95% Confident Interval of the difference in proportions, $\pi_T - \pi_S > -0.10$) with 80% power and by applying a two-group large-sample normal approximation test of proportions with a one-sided 0.025 significance level, assuming that the expected difference in proportions is 0 and the proportion in the standard group is 0.64.⁴⁷

The total sample size (362 + 362 = 724) is adjusted to 800 patients considering an expected dropout rate of about 10% using Freedman's formula⁴⁸: n'= 100*n/100-x, where x is the expected dropout rate.

9.3 POPULATIONS FOR ANALYSES

The following populations have been defined for analysis:

- Safety set: all randomized patients who take at least one dose of study treatments.
- Full Analysis Set (FAS): all randomized patients who take at least one dose of study treatment. According to the Intention to Treat (ITT) principle, patients who discontinue the study treatment are considered as failures. Appropriate methods for the replacement of missing values will be detailed in the statistical analysis plan.
- Per protocol (PP) set: All randomized patients who do not have significant protocol violations that regard inclusion/exclusion criteria or that can condition efficacy evaluations, including the use of rescue medication.

The efficacy analyses will be performed on the FAS, having those on the PP population as supportive. The safety and tolerability analyses will be performed on the Safety population.

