6.3 MEASURES TO MINIMIZE BIAS: RANDOMIZATION AND BLINDING

This is a randomized, blinded-assessor study. Patients will be assigned to one of the two following treatment groups in 1:1 ratio according to a randomization list stratified by center:

- Test arm: levofloxacin + dexamethasone ophthalmic solution for 7 days followed by dexamethasone ophthalmic suspension (Maxidex[®]) alone for an additional 7 days
- Control arm: tobramycin 3 mg/ml + dexamethasone 1 mg/ml (Tobradex[®]) ophthalmic suspension for 14 days

The randomization numbers will be generated using procedures that ensure that treatment assignment is unbiased. A patient randomization list will be produced using a validated system that automates the assignment of randomization numbers.

Patients who fulfill all inclusion criteria and none of the exclusion criteria will be randomized following surgery via an Interactive Web Response System (IWRS) that will assign the patient a

randomization number linked to a treatment arm. Unblinded staff is to use the IWRS to obtain the study treatment to be given to the patient.

The physician in charge of assessing study parameters will be blinded to treatment assignment (blinded assessor). The blinded assessor will not have access to the randomization page of the eCRF. A separate investigational staff will be unblinded and responsible for assigning and dispensing/return study products. Study treatment will be dispensed upon randomization and on Day 8.

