6.5.1 PROHIBITED CONCOMITANT THERAPY

The following treatments are not permitted:

- Topical antibiotics
- Systemic antibiotics for prophylactic purposes
- Topical or systemic steroids

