6.5.2 RESCUE THERAPY

Rescue therapy is defined as the introduction or dose modification of any local or systemic nonrandomized medication required to manage the emergence or worsening of ocular inflammation and or infection.

The name and dosage regimen of the rescue medication as well as the date and time of administration must be recorded in the eCRF.

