In those diseases causing thinning of the cornea or sclera, perforations have been known to occur with the use of topical corticosteroids.

Benzalkonium chloride used as a preservative may cause irritation of the eye.

Maxidex®

Both topical corticosteroids and NSAIDs may slow corneal healing. Caution is therefore advised when using topical dexamethasone and topical NSAIDs concomitantly.

Prolonged use of topical ophthalmic corticosteroids may result in ocular hypertension/glaucoma with resultant damage to the optic nerve and reduced visual acuity and visual fields defects. It is advisable that intraocular pressure be checked frequently. The risk of corticosteroid-induced raised intraocular pressure is increased in predisposed patients (e.g. diabetes).

Corticosteroids may reduce resistance to and aid in the establishment of bacterial, viral and fungal infections and mask the clinical signs of infections. In such cases antibiotic therapy is

Maxidex®

mandatory. Fungal infection should be suspected in patients with persistent corneal ulceration and corticosteroids therapy should be discontinued if fungal infection occurs.

In those diseases causing thinning of the cornea or sclera, perforations have been known to occur with the use of topical corticosteroids.

Benzalkonium chloride used as a preservative may cause irritation of the eye.

Levofloxacin/dexamethasone

Both topical corticosteroids and NSAIDs may slow corneal healing. Caution is therefore advised when using topical dexamethasone and topical NSAIDs concomitantly.

Systemic fluoroquinolones have been associated with hypersensitivity reactions, even following a single dose. If an allergic reaction does occur, discontinue the medication.

As levofloxacin is phototoxic at very high doses and photosensitization may not be excluded, patients should not be exposed to direct sunlight during treatment.

Prolonged use may result in overgrowth of non-susceptible organisms, including fungi. If worsening of infection occurs, or if a clinical improvement is not noted within a reasonable period, discontinue use and institute alternative therapy.

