7 STUDY INTERVENTION DISCONTINUATION AND PARTICIPANT DISCONTINUATION/WITHDRAWAL

7.1 DISCONTINUATION OF STUDY INTERVENTION

Treatment may be discontinued permanently, regardless of treatment arm, if any adverse event, medical condition or situation warrants discontinuation of treatment. The following situations call for permanent discontinuation of study treatments as per SPC/IB:

Tobradex®
Hypersensitivity to Tobradex [®] .
Cushing's syndrome and/or adrenal suppression.
Fungal infections.

Maxidex®

Fungal infections.

Levofloxacin/dexamethasone
Allergic reactions.
Worsening of infection or lack of clinical improvement.
Fungal infections.

Discontinuation from treatment does not mean discontinuation from the study, and remaining study procedures should be completed as indicated in the study protocol. If a clinically significant finding is identified after enrollment, the investigator will determine if any change in participant management is needed. Any new clinically relevant finding will be reported as an adverse event (AE).

Patients discontinuing treatment will be asked to undergo the assessments planned for the End of Study (EOS) Visit (see the SoA in *Section 1.3*).

Temporary treatment interruptions and dose modifications are not foreseen in the protocol. See *Section 6.1.2.1* for information concerning the management of missed doses.

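### The primary analysis can count a rescued patient as a success: the FAS scores only stopping study drug as failure, and no planned analysis scores rescue as failure

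*Combined protocol and SAP*

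**What the plan says.** **Endpoint and analysis set.** Section 9.4.2 defines success as a cells plus flare score of 0 after 14 days and does not mention rescue. Section 9.3 makes the FAS the main efficacy set, with PP supportive. Invoking the intention-to-treat principle, it says that "patients who discontinue the study treatment are considered as failures". It leaves the replacement of missing values to a statistical analysis plan that is not in the supplied text.

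**Rescue.** Section 6.5.2 defines it as "the introduction or dose modification of any local or systemic nonrandomized medication required to manage the emergence or worsening of ocular inflammation" or infection. Drug, regimen, date and time must be recorded. The section does not say whether study drug then continues or stops, and it sets no threshold for starting rescue.

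**PP set.** Section 9.3 admits patients without significant violations of the entry criteria or violations "that can condition efficacy evaluations, including the use of rescue medication".

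**Stopping.** Section 7.1 is discretionary in general: "Treatment may be discontinued permanently, regardless of treatment arm", where an event or situation warrants it. Patients who stop stay in the study, so a Day 15 score can exist for them.

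**Rescue as an outcome.** Section 9.4.3 reports the proportion using rescue with a 95% confidence interval. Section 9.1 tests no hypothesis on secondary endpoints.

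**The concern.** Rescue is given because ocular inflammation or infection has appeared or worsened, which is what the trial sets out to prevent and treat. If the added drug clears the eye by Day 15 and study drug was never stopped, the plan records a success for study drug. If rescue is more frequent in the test arm, the difference moves toward non-inferiority for a reason unrelated to the test product. If it is more frequent in the control arm, the shift goes the other way.

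The plan is also uneven in its own terms. Stopping study drug is a failure whatever the Day 15 eye looks like. Needing another drug for the target condition has no consequence. Two patients with the same rescue and the same clear eye can score differently because one was taken off study drug.

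**Working it through.** **1. How each rescued patient with a Day 15 score is classified**

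| Patient | FAS (9.3, 9.4.2) | PP (9.3) |
|---|---|---|
| Rescued, study drug continued, score 0 | success | excluded |
| Rescued, study drug stopped, score 0 | failure | excluded |
| Rescued, score above 0 | failure | excluded |

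Neither column treats rescue itself as failure. The reference to a later analysis plan concerns missing values, and a rescued patient with a Day 15 score is not missing.

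**2. The plan's own figure.** Inputs from 9.1 and 9.2: success 0.64 in both arms, margin 0.10, one-sided 0.025, power 80%.
n = (1.96 + 0.8416)² × 2 × 0.64 × 0.36 / 0.01 = 361.7, so 362 per arm. This agrees with 9.2 and is not in dispute.

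**3. Chance of declaring non-inferiority at the margin.** The rescue rates and the share of rescued patients clear on Day 15 (c = 0.64) are assumptions. Take 400 per arm and true success with rescue as failure of 0.54 versus 0.64. All rescued patients stay on study drug.

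- Rescue 5% (test) versus 2% (control). Scored as the plan reads, the rates become 0.54 + 0.05 × 0.64 = 0.572 and 0.64 + 0.02 × 0.64 = 0.6528, a difference of -0.0808.
- SE = √(0.572 × 0.428/400 + 0.6528 × 0.3472/400) = 0.0343.
- Probability = Φ((-0.0808 + 0.10)/0.0343 - 1.96) = Φ(-1.40) = 8.1%, against 2.5%.

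The same formula gives:

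| Rescue, test v control | c | Chance of declaring non-inferiority |
|---|---|---|
| 5% v 2% | 0.30 | 4.5% |
| 5% v 2% | 0.50 | 6.4% |
| 5% v 2% | 0.64 | 8.1% |
| 5% v 2% | 0.80 | 10.4% |
| 8% v 4% | 0.64 | 11.3% |
| 10% v 5% | 0.64 | 15.5% |
| 5% v 5% | 0.64 | 2.5% |
| 2% v 5% | 0.64 | 0.6% |

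**4. Worked results.** Wald 95% intervals in percentage points, 400 per arm. About 64% of rescued patients are clear: 13 of 20 and 5 of 8.

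- As the plan reads, all continuing: 248 v 256 gives -2.0 (-8.7 to 4.7), non-inferior.
- Rescue 20 v 8 scored as failure: 235 v 251 gives -4.0 (-10.8 to 2.8), not shown.
- From equal results, 256 v 256 gives 0 (-6.7 to 6.7). With 20 v 8 as failures, 243 v 251 gives -2.0 (-8.7 to 4.7), still non-inferior.
- Rescue 20 v 20 scored as failure from 248 v 256: 235 v 243 gives -2.0 (-8.8 to 4.8). The lower bound moves by 0.1 point.

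For 20 v 8 the 9.4.3 rescue endpoint would show +3.0 points (0.5 to 5.5). Unequal rescue would be visible, but it would not enter the decision.

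**The case against.** **The scoring is determinate.** A reader might infer that no rule covers rescued patients. That goes too far. Study-drug stoppers are failures and everyone else with a Day 15 score takes that score. Ignoring rescue is a recognised choice under intention to treat, and on that scale the 5% v 2% case has a true difference of -8.1 points, inside the margin. The 8% is therefore a false claim only if rescue ought to count as failure. What remains is that 9.3 does not follow that approach consistently: it fails stoppers even when the eye is clear.

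**Arm-dependent stopping is not established.** A reader might infer it from two places.
- Section 7.1 lists "Worsening of infection or lack of clinical improvement" for levofloxacin/dexamethasone alone, and 6.6 says to "discontinue use and institute alternative therapy". In 6.6 this reads mainly as an infection warning, for a product used only in the first 7 days. The one infection rate given, endophthalmitis at 0.03–0.3% (2.2), is about 0.1 to 1.2 patients per 400.
- Section 6.3 says "A separate investigational staff will be unblinded and responsible for assigning and dispensing/return study products". It does not say that these staff decide on rescue or on stopping, so arm-informed stopping is conjecture.

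**Extreme power figures.** With 5% rescue in both arms, c = 0.64 and no true difference, power at 400 per arm is 84%. It falls to 51% if every rescued test patient and no rescued control patient stops, and rises to 97% in the reverse case. These need all-or-none stopping by arm and are bounds only. At 60% v 40% stopping, power is 78%.

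**Unequal rescue has no stated basis.** Both arms use the same dexamethasone strength (4.2), and rescued patients may clear less often than 64%. Both points stand and limit the expected size.

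**Other safeguards.** Section 9.4.4 lists adverse events leading to discontinuation, and 9.4.10 plans patient listings. The separate analysis plan may address rescue; that cannot be known from the text supplied. None of this puts rescue into the stated primary analysis.

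**Conclusion.** The point holds in this form: as written, the FAS primary analysis can count a rescued patient as a success, and no planned analysis counts rescue as failure. The size cannot be fixed from the documents because they give no rescue rate. Under the assumptions in step 3, 5% v 2% rescue raises the chance of declaring non-inferiority at a true -10 points from 2.5% to about 8%. The range is 4.5% to 10.4% as the share clear runs from 30% to 80%. With equal rescue handled alike the effect is close to nil, and with more rescue in the control arm the error runs against the test product. This is a cheap improvement to the plan, not a reason to think that the trial must mislead.

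**What to change.** In 9.3 or 9.4.2, state that a FAS patient who receives rescue therapy as defined in 6.5.2 before the Day 15 assessment is a failure, whether or not study drug was stopped. Add the observed Day 15 score regardless of rescue as a sensitivity analysis. State one rule for both arms on whether study drug continues after rescue. Separately, 6.5.1 introduces its list (topical antibiotics, prophylactic systemic antibiotics, steroids) with "The following treatments are not permitted" and makes no exception for rescue; adding one is editorial.

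**Cost.** A few sentences and no new data, since 6.5.2 already records drug, date and time. At an assumed 5% rescue in both arms:
- The planning rate falls to 0.64 - 0.05 × 0.64 = 0.608.
- Required n = (1.96 + 0.8416)² × 2 × 0.608 × 0.392 / 0.01 = 374.1, so 375 per arm instead of 362.
- Power at 400 per arm is 83% instead of 84%. At 360 evaluable per arm (400 less 10%) it is Φ(0.10/√(2 × 0.608 × 0.392/360) - 1.96) = 78% instead of 80%.

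The change also moves some discretion. The outcome then depends on the decision to start rescue, for which 6.5.2 gives no threshold, and an added NSAID, which 6.5.1 does not prohibit, would count if given for inflammation. A short criterion for starting rescue would limit this.

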9.4 STATISTICAL ANALYSES

9.4.1 GENERAL APPROACH

Continuous data will be summarized with standard descriptive statistics (i.e. the mean, standard deviation, minimum, median and maximum, 95% confidence limits). Categorical data will be summarized by frequencies and percentages.

No statistical test will be performed for between-group differences in demographic and baseline features (medical history and efficacy data).

Medical history and adverse events will be described according to System Organ Classes (SOC) and Preferred Terms (PT) using the Medical Dictionary for Regulatory Activities (MedDRA) and will be presented by treatment group.

Previous/concomitant medications will be presented by treatment group using the World Health Organization Drug Dictionary (WHO-DD).

All analysis will be performed using SAS version 9.4 or later.

9.4.2 ANALYSIS OF THE PRIMARY EFFICACY ENDPOINT(S)

The proportion of patients without signs of anterior chamber inflammation (sum of cells and flare score = 0) after 14 days of treatment will be calculated to evaluate the non-inferiority of the test

treatment vs. the standard therapy. Non-inferiority will be assessed by computing the two-tailed 95% confidence interval (CI) of the difference between the two proportions $\pi_T - \pi_S$. Non-inferiority is met if the 95% CI does not cross the predefined non-inferiority margin $\Delta = -0.10$ and lies entirely to the right of the margin (i.e. non-inferiority will be demonstrated if the lower bound of the two-sided 95% CI of the difference is > -0,10).

If the 95% CI of the difference lies completely to the right of 0, the test treatment can be considered more effective than the standard treatment at a 5% significance level.

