2.2 BACKGROUND

Cataract is an ocular condition that causes vision impairment due to changes in opacity of the ocular lens. Cataract is an age-related condition, but smoking, ocular trauma, exposure to ultraviolet light, diabetes and drug-induced metabolic changes in the lens are risk factors for lens opacification causing cataract.¹

The only cure for cataract is a surgical procedure: the opaque lens is removed and replaced with an artificial intraocular lens.^{2, 3} Nowadays, the surgical procedure of choice is phacoemulsification with intraocular lens implantation.⁴ The technique, initially developed in 1967, is based on high-energy ultrasound to emulsify the cataractous lens nucleus, with the fragments being subsequently aspirated with an ultrasound probe. The corneal incision required for this technique is much

smaller (3 mm or less) than the limbal incision (usually an 11-mm incision between cornea and sclera) used in the past to remove the entire lens.²

As the surgical procedure has become less invasive, patients usually no longer require in-patient hospital care after surgery, with recovery usually uneventful and pain-free. Cataract surgery may however cause corneal trauma, ocular inflammation and ocular dryness, which can result in ocular irritation during the recovery period.⁵⁻⁷ These conditions may cause different types of ocular discomfort such as pain, burning, stinging, foreign body sensation, itchiness and glare in the operated eye. The incidence of ocular irritation symptoms experienced during the first postoperative hours may be as high as 98%.⁸

Conjunctival hyperemia, anterior chamber cells and flare, and cystoid macular edema are some possible signs of inflammation after cataract surgery.⁹ The severity of the inflammation varies from patient to patient. In many cases, inflammation is self-limiting, but drug therapy is used to shorten resolution time and alleviate ocular discomfort.¹⁰

Steroidal agents and non-steroidal anti-inflammatory drugs (NSAIDs) are used to prevent and treat postoperative inflammation occurring after surgery. Corticosteroids inhibit the lipoxygenase pathway leading to the leukotriene production and thus reduce tissue swelling and prevent edema.^{9,11} They have been used for decades to prevent ocular inflammation and many ophthalmic surgeons prefer a 1 to 6-week period of topical corticosteroids after cataract surgery.

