8.2 EFFICACY ASSESSMENTS

• Slit lamp examination

A slit lamp examination will be performed at Visit 1 (screening) and on Day 4 (Visit 3), Day 8 (Visit 4), and Day 15 (Visit 5) to evaluate cells in the anterior chamber and aqueous flare as follows:

Cells in anterior chamber: results are to be provided as a score: 0 = no cells; 1 = 1-5 cells; 2 = 6-15 cells; 3 = 16-30 cells; 4 = >30 cells.⁴⁸

Aqueous flare (Tyndall effect): results are to be provided as a score: 0 = absent; 1 = trace barely detectable; 2 = mild intensity (iris and lens details clear); 3 = moderate intensity (iris and lens details not clear); 4 = strong intensity (iris and lens details not visible and fibrin in the anterior chamber).⁴⁴

Conjunctival hyperemia will be evaluated and results provided as a score as follows: 0 = absence of inflammation, 1 = mild inflammation (some vessels injected), 2 = moderate inflammation (diffuse injection of vessels, but individual vessels are still discernable) 3 = severe inflammation (intense injection of vessels, individual vessels not easily discernable).⁴⁵

• Endophthalmitis

All cases of endophthalmitis occurring following cataract surgery are to be reported at all visits.

• Total Ocular Symptom Score (TOSS)

The TOSS is a patient-reported evaluation of 3 ocular symptoms: itching/burning, hyperemia of conjunctiva and tearing. Each symptom is given a score: 0 = none, 1 = mild, 2 = moderate, 3 = severe. The TOSS will be evaluated on Days 4, 8, and $15.^{46}$ See Appendix 1.

• Ocular pain/discomfort

Overall ocular pain and discomfort will be evaluated by the subject at Days 4, 8 and 15 on a 4-point scale (0 = absent, 1 = mild, 2 = moderate, 3 = severe).

• Use of rescue therapy

All rescue therapy used following cataract surgery is to be reported at all visits (see *Section 6.5.2*).

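### The primary risk difference uses no patient-level baseline; prespecified adjustment for age, and possibly diabetes history, might narrow the interval at almost no cost

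*Combined protocol and SAP*

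**What the plan says.** Section 9.4.2 defines the primary analysis: "Non-inferiority will be assessed by computing the two-tailed 95% confidence interval (CI) of the difference between the two proportions". The decision rule is that "non-inferiority will be demonstrated if the lower bound of the two-sided 95% CI of the difference is > -0,10". The section names no covariate, no stratification factor and no adjusted sensitivity analysis.

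Section 9.2 sizes the trial for the same unadjusted comparison, at a "one-sided 0.025 significance level", assuming that "the expected difference in proportions is 0" and that "the proportion in the standard group is 0.64".

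Baseline data are collected. The schedule in section 1.3 and the visit list in section 8.1 put demography and medical history at Visit 1. Section 8.2 adds that "A slit lamp examination will be performed at Visit 1 (screening") and again on Days 4, 8 and 15. Sections 9.4.1 and 9.4.7 use baseline data for description only. Section 9.3 leaves missing-value methods to a statistical analysis plan, but the documents available contain no separate plan text that names covariates.

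**The concern.** One lower confidence bound decides the trial, and the planned power is only 80%. Section 2.2 says of inflammation after cataract surgery that "The severity of the inflammation varies from patient to patient". Eligibility is broad: age 40 and over with no upper limit, at about 80 centres in four countries. If some of the variation in Day 15 clearance can be predicted from data already recorded, the crude interval leaves that information unused.

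A standardised risk difference averages model-predicted clearance under each treatment over all patients. It targets the same marginal difference as the crude estimate, so the margin and the decision rule carry over unchanged. What is at stake is interval width, and with it some power. The validity of the conclusion is not in question.

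**Working it through.** **Inputs.** From sections 9.2 and 9.4.2: proportion 0.64 in both arms, margin 0.10, one-sided 0.025, power 80%. Assumed, because no document gives it: R², shown from 0 to 10%.

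**The plan's own figure.** n = 2 × 0.64 × 0.36 × (1.960 + 0.842)² / 0.10² = 361.7, rounded up to 362 per arm. This matches section 9.2 and involves no covariates.

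**Effect of adjustment.** To a good approximation SE = √(2 × 0.64 × 0.36 × (1 − R²) / n). The half-width is 1.96 × SE and power is Φ(0.10/SE − 1.96). Section 9.2 plans for 362 evaluable per arm; 400 is the number randomised per arm.

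| R² | Half-width, n = 362 (points) | Power, n = 362 | Power, n = 400 | n per arm for 80% power |
|---|---|---|---|---|
| 0 | 6.99 | 80.0% | 83.8% | 362 |
| 2% | 6.92 | 80.8% | 84.5% | 355 |
| 5% | 6.82 | 82.0% | 85.6% | 344 |
| 10% | 6.63 | 84.0% | 87.4% | 326 |

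At R² = 5%, 362 adjusted patients per arm are worth 362/0.95 = 381 unadjusted.

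**What R² would take.** For a covariate that shifts the success rate by b per standard deviation, R² = b² / (0.64 × 0.36). Shifts of 5, 10 and 15 points give R² of 1.1%, 4.3% and 9.8%. Nothing in the documents says where age or diabetes history falls on this scale.

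**The screening score.** Suppose a share q of eyes has a non-zero score and a success rate lower by d. Then R² = q(1 − q)d² / 0.2304. Both inputs are assumptions. With q = 1 to 2% and d = 20 to 30 points, R² is 0.2 to 0.8% and the interval is 0.1 to 0.4% narrower. With q = 10% and d = 30 points, it is 1.8% narrower.

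**Validity and cost.** Simulation used 8,000 trials per setting, 362 per arm, and linear adjustment with a robust standard error as a stand-in for g-computation.
- At a true difference of -0.10, one-sided error was 2.5 to 2.8% unadjusted and 2.6 to 2.7% adjusted.
- At no true difference, power rose from 80.4% to 82.2% with R² near 5%, and from 79.4% to 83.5% with R² near 10%.
- With a useless covariate, the mean half-width went from 6.983 to 6.997 points, a widening of about 0.015.

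**Chance imbalance.** The standard deviation of the between-arm difference in a standardised covariate is √(2/362) = 0.074. A covariate worth 5 points per standard deviation therefore moves the estimate by about 0.37 points, and one worth 10 points by about 0.74. The crude half-width is 6.99.

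**The case against.** The strongest case against a change is that the plan is coherent as written. The sample size and the analysis use the same unadjusted comparison, the interval is on the scale of the margin, and the stated power needs no covariates. All of that stands.

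It is also fair that the documents link neither age nor diabetes to Day 15 clearance. Diabetes appears in section 2.2 as a risk factor for cataract and in section 6.6 as a predisposition to steroid-induced pressure rise, and diabetic retinopathy is among the exclusion examples in section 5.2. The remark on varying severity says nothing about what predicts it. So nothing places R² at 5 or 10% rather than near 0, and any gain is conditional.

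A reader might be tempted by the screening cells and flare score as the baseline of the primary endpoint. The documents do not support that. The score is taken up to 28 days before the surgery that causes the inflammation, and section 5.2 lists uveitis and keratitis among the conditions excluded at the investigator's discretion. No criterion requires a score of 0, but nearly all eligible eyes should have one. A near-constant covariate adds almost no precision and could cause sparse-data problems in a logistic model. No slit lamp examination is scheduled between surgery and Day 4, so no post-operative, pre-treatment score exists.

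Centre is a separate question. Allocation is in a "1:1 ratio according to a randomization list stratified by center", yet centre is also absent from the primary analysis. With 800/80, or about 10 patients per centre, adjusting for it would need its own rule for small centres. That gap does not answer the point about patient-level baselines.

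**Conclusion.** The point holds as an optional efficiency improvement of low weight. The primary analysis uses no patient-level baseline, and a prespecified adjusted risk difference would keep the estimand, the margin and the error rate. On the assumed range, the gain at 362 per arm runs from nil at R² = 0 to 2.0 power points at 5% and 4.0 at 10%. If the covariates prove useless, the loss is negligible but not exactly zero.

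Two stronger readings should be avoided. A reader might infer that the crude interval is wider than it need be as a matter of fact; without a document-based R², only *may be* is justified. A reader might also infer that uncorrected chance imbalance biases the result. Under randomisation the crude interval already allows for that variation and keeps its error rate.

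The power figures rest on the plan's 0.64 in both arms and on the normal approximation.

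**What to change.** In section 9.4.2, and in the statistical analysis plan:

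- Make the primary estimate a standardised (g-computation) marginal risk difference from a logistic model with treatment and a short covariate list fixed before unblinding. The list is age, plus diabetes history if it is common enough, judged on pooled blinded data against a stated threshold.
- Prespecify the 95% interval method (robust or bootstrap), a simple rule for missing covariates, and what is done if the model does not converge.
- Keep the rule that the lower bound must exceed -0.10.
- Keep the crude difference in proportions as a sensitivity analysis.
- Leave the screening cells and flare score out of the model.

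The cost is a paragraph of wording and a little programming. No new data or visits are needed, and the sample size stays as it is.
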